7.2 Required Observations Following Completion of Protocol Therapy

Observation	3 Months, 6 Months, 9 Months	Every 4 Months up to 24 Months (Months 12, 16, 20, 24) and at 30 Months	Annually up to 60 Months (Months 36, 48, 60)	At Relapse
Physical Exam with neurologic exam	X	X	X	X
Brain MRI with and without gadolinium	X	X	X	X
Spine MRI with gadolinium	X	X	X	X
Serum markers (hCG, AFP)	X	X	X	X
Lumbar CSF markers and cytology				X
Endocrine evaluation ⁴			X	
Audiogram or BAER		X ²	X ²	
Neurocognitive Function (See ALTE07C1 Protocol and Section 16.0)	X ³	X ³	X ³	

1 - Lumbar CSF cytology and markers and serum markers should be obtained only at time of relapse unless medically contraindicated or if abnormal at completion of therapy.

2 - Obtain if clinically indicated or if abnormal at completion of therapy.

3 - Obtain at 9 months (± 3 months), 30 (± 3 months) and 60 months (± 3 months) post diagnosis.

4 - Endocrine evaluation to include: Cortisol (8 AM), TSH, free T4, IGF1 and IGF BP3. Tanner Stage, LH, FSH, Estradiol, and Testosterone if child has precocious puberty before age 8 in girls or 9 in boys or for all patients age 11 or greater.

See COG Late Effects Guidelines for recommended post treatment follow-up:

<http://www.survivorshipguidelines.org/>

Note: Follow-up data are expected to be submitted per the Case Report Forms (CRFs) schedule.

8.0 CRITERIA FOR REMOVAL FROM PROTOCOL THERAPY AND OFF STUDY CRITERIA

8.1 Criteria for Removal from Protocol Therapy

- a) Progressive disease with increasing markers during Induction chemotherapy.
- b) NGGCT (Stratum 1) patients with positive markers at the end of Induction chemotherapy or who have < PR after induction chemotherapy.
- c) NGGCT (Stratum 1) patients with < PR after second-look surgery or any viable tumor (except mature teratoma) after second-look surgery
- d) NGGCT (Stratum 1) patients who are unable to undergo second-look surgery due to safety or other reasons and do not meet criteria for CR/PR (imaging and tumor markers).
- e) Germinoma (Stratum 2) patients with PD and positive markers at the end of Induction chemotherapy.
- f) Germinoma (Stratum 2) patients who are unable to undergo second-look surgery due to safety concerns and they do not meet the criteria for at least PR with ≤ 1.5 cm residual disease without second-look surgery.
- g) Germinoma (Stratum 2) patients with any viable tumor (except mature teratoma, fibrosis, scar or non-viable tumor) after second-look surgery
- h) Refusal of further protocol therapy by patient/parent/guardian.
- i) Completion of protocol therapy.
- j) Physician determines it is in patient's best interest.
- k) Development of a second malignancy.
- l) Patient is enrolled but rechecked labs are outside the limits of eligibility prior to starting therapy. (See [Section 3.2](#))
- m) Radiotherapy cannot be initiated within 6 weeks after Day 1 of the last cycle of Induction chemotherapy or within 31 days after second-look surgery. (See [Sections 15.2.3](#) and [15.2.4](#)).
- n) Progressive disease with positive or increasing markers at the end of Induction chemotherapy, following second-look surgery or during radiation therapy.

Patients who are off protocol therapy are to be followed until they meet the criteria for Off Study (see below). Follow-up data will be required unless consent was withdrawn.

8.2 Off Study Criteria

- a) Death.
- b) Lost to follow-up.
- c) Patient enrollment onto another COG study with tumor therapeutic intent (eg, at recurrence).
- d) Withdrawal of consent for any further data submission.
- e) The fifth anniversary of the date the patient was enrolled on this study.
- f) Patient did not receive protocol treatment after study enrollment.

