1.2 Secondary Objectives

1.2.1

To estimate the PFS and overall survival (OS) distributions of patients with NGGCT treated with 30.6Gy WVI and involved field focal (IFR) boost to 54Gy.

1.2.2

To estimate the PFS and OS distributions of localized germinoma patients who present with **a)** serum and/or CSF hCG β ≤ 50 mIU/ml and **b)** serum and/or CSF hCG β > 50 mIU/ml and ≤ 100 mIU/ml.

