3.0 STUDY ENROLLMENT PROCEDURES AND PATIENT ELIGIBILITY

3.1 Study Enrollment

3.1.1 Patient Registration

Prior to enrollment on this study, patients must be assigned a COG patient ID number. This number is obtained via the COG Registry system once authorization for the release of protected health information (PHI) has been obtained. The COG patient ID number is used to identify the patient in all future interactions with COG. If you have problems with the registration, please refer to the online help.

In order for an institution to maintain COG membership requirements, every newly diagnosed patient needs to be offered participation in ACCRN07, *Protocol for the Enrollment on the Official COG Registry, The Childhood Cancer Research Network (CCRN)*.

A Biopathology Center (BPC) number will be assigned as part of the registration process. Each patient will be assigned only one BPC number per COG Patient ID. For additional information about the labeling of specimens please refer to the Pathology and/or Biology Guidelines in this protocol.

Please see [Appendix I](#) for detailed CTEP Registration Procedures for Investigators and Associates, and CTSU Registration Procedures including: how to download site registration documents; requirements for site registration, submission of regulatory documents and how to check your site's registration status.

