Assessing neurocognitive function for patients treated on ACNS1123 will be considered feasible unless statistical evidence develops that fewer than 80% of patients who are eligible and evaluable for assessing primary objectives 1.1.1 or 1.1.2 and who are failure free at three years post initiation of therapy can be expected to have both 9-month and 30-month neurocognitive assessments on ALTE07C1. This rate of success will ensure that longitudinal modeling of neurocognitive function will provide viable historical controls for subsequent COG trials of these diseases. The rate of also achieving 60-month (5-year) neurocognitive assessments is not considered for monitoring feasibility, as the total study duration is only expected to be approximately seven years.

The statistical criteria for monitoring neurocognitive evaluations are based on a one-sided test ($\alpha = 0.025$) that the true, unknown, success rate is at least 80% ($\geq 80\%$) with 80% statistical power to detect that the success rate is 65%, which would be unacceptable. Assuming a binomial distribution, EAST5 was used to calculate the two stopping boundaries. If within a stratum, 9 (≤ 9) or fewer of the first 23 patients evaluable for feasibility (39.1%) have both 9 and 30 month evaluations (i.e. patients who are eligible and evaluable for assessing the primary objective and are more than 30 ± 4 months from

diagnosis), we will recommend to the COG DSMB that consideration be given to closing the stratum. The second boundary for recommending closing the stratum will be if 28 or fewer (≤ 28) of the initial 45 patients evaluable for feasibility (62.2%) enrolled in that stratum have both 9 and 30 month evaluations (i.e. patients who are eligible and evaluable for assessing the primary objective and are more than 30 ± 4 months from diagnosis). Otherwise accrual to the stratum will continue until the full cohort of patients required to address the primary objective assessing the 3-year progression-free survival rate has been achieved.

Our ability to address the secondary objectives depends upon whether the proposed treatment regimen is effective or not. Secondary objectives will be reported descriptively and as exploratory. Other than reports requested by the COG DSMB, secondary objectives will only be analyzed at the end of the trial.

1. The first secondary objective is to provide Kaplan-Meier estimates of distributions of PFS and overall survival for NGGCT patients.

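### Going off study on joining another COG treatment study censors some relapsed patients at relapse and biases the exploratory overall survival estimates upward

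*Combined protocol and SAP*

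**What the plan says.** Secondary objective 1.2.1 is "To estimate the PFS and overall survival (OS) distributions of patients with NGGCT treated with 30.6Gy WVI" and boost. Objective 1.2.2 asks for the same two distributions in two germinoma cohorts defined by hCGβ at presentation. Section 9.1 plans to "provide Kaplan-Meier estimates of distributions of PFS and overall survival for NGGCT patients", with matching wording for the germinoma cohorts, and calls the secondary objectives descriptive and exploratory.

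On follow-up, Section 8.1 states: "Patients who are off protocol therapy are to be followed until they meet the criteria for Off Study". It adds: "Follow-up data will be required unless consent was withdrawn". Both sentences concern patients off protocol therapy; neither reaches past the off-study date. Section 8.2 lists the off-study criteria. One is administrative: "The fifth anniversary of the date the patient was enrolled on this study". Criterion (c) is "Patient enrollment onto another COG study with tumor therapeutic intent (eg, at recurrence"). Section 7.2 has a relapse visit but lists no survival follow-up after a patient goes off study. The documents state no censoring rule for OS, no retrieval of vital status from the later study and no sensitivity analysis.

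**The concern.** Kaplan-Meier assumes that a patient censored at a given time has the same later prognosis as those still at risk. Criterion 8.2(c), by its own example, removes patients who have just relapsed, and these patients carry much of the remaining risk of death. The estimator then gives them the average survival of everyone still followed, most of whom are relapse-free. This is informative censoring produced by a written rule, not by accidental loss.

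The trial reduces radiation dose and volume. Section 2.2 supports this in germinoma partly by noting that most relapses can be salvaged. PFS cannot show whether that holds; OS can, and the rule removes deaths from the patients who would show it. The PFS endpoint is protected, because Section 9.3 counts a missing 3-year status as failure. OS has no such protection.

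**Working it through.** **The plan's own figures.** No design figure is given for OS. The primary designs reproduce by exact binomial:
- Stratum 1, at least 69 of 77: P(X ≥ 69) = 0.0492 at 0.82 and 0.911 at 0.93, as stated.
- Stratum 2, at least 73 of 79: 0.098 at 0.87 (target 0.10) and 0.900 at 0.95 (target 0.90).

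These tests do not change. A relapse is already a PFS failure before 8.2(c) can apply to it.

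**Inputs for OS.**
- r, the share relapsing by 3 years: 0.07 and 0.18 in Stratum 1, 0.05 and 0.13 in Stratum 2 (one minus the alternative and null PFS rates in Sections 9.3.1 and 9.3.2).
- m, mortality after relapse: assumed, 0.25 to 0.70. The middle value of 0.45 is a rough guide from the 2-year ACNS0122 rates in Section 2.1.2: (100 − 93)/(100 − 84.4) = 7.0/15.6 = 0.45.
- q, the share of relapsed patients who join another COG treatment study: assumed, 0 to 0.75.

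**Formula.** Suppose that every death follows a relapse and that, for simplicity, all relapses come before the deaths. Per patient enrolled, a fraction qr is censored, 1 − qr stays at risk and rm(1 − q) die under observation. Then:
- true OS = 1 − rm
- Kaplan-Meier OS = 1 − rm(1 − q)/(1 − qr)
- bias = rmq(1 − r)/(1 − qr)

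Example with r = 0.07, m = 0.45, q = 0.50: true OS = 1 − 0.0315 = 96.9%; bias = 0.0315 × 0.50 × 0.93/0.965 = 0.0152, or 1.5 points.

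**Result.** A simulation with staggered times (75% of relapses in year 1, the rest in year 2, deaths within a year of relapse) agrees with the formula to within about 0.2 points. Simulated upward bias in 3-year OS at m = 0.45, in percentage points:

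| Stratum, 3-year PFS | q = 0 | 10% | 25% | 50% |
|---|---|---|---|---|
| 1, 0.93 (alternative) | 0 | 0.3 | 0.7 | 1.5 |
| 1, 0.82 (null) | 0 | 0.7 | 1.8 | 3.8 |
| 2, 0.95 (alternative) | 0 | 0.2 | 0.6 | 1.1 |
| 2, 0.87 (null) | 0 | 0.5 | 1.3 | 2.8 |

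The bias is proportional to m: multiply by 0.25/0.45 = 0.56 or 0.70/0.45 = 1.56 for the ends of the range. At q = 75% and m = 0.45 the formula gives 2.3, 5.8, 1.7 and 4.2 points, in row order. At q = 100% it gives bias = rm, so the whole mortality disappears and the curve reads 100%.

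**Against precision.** The standard error of OS is √(0.969 × 0.031/77) = 2.0 points in Stratum 1 at PFS 0.93, and √(0.9775 × 0.0225/79) = 1.7 points in Stratum 2 at 0.95. The 79 is illustrative, because the sizes of the 1.2.2 cohorts are not given. In patients, Stratum 1 at 0.93 expects 77 × 0.07 = 5.4 relapses and 5.4 × 0.45 = 2.4 deaths, of which 0.6 are lost at q = 25% and 1.2 at q = 50%.

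**Five years.** A second simulation (relapses between 0.3 and 2 years, m read as 2-year mortality after relapse, later deaths included) gives, for q = 25% and 50% at m = 0.45, 1.1 and 2.3 points in Stratum 1 at PFS 0.93, and 0.8 and 1.7 points in Stratum 2 at 0.95.

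**The case against.** The strongest reply is that little hangs on this. OS has no test, threshold or stopping rule. The share joining appears nowhere in the documents, and no section says that a COG relapse trial for these tumors exists. If few patients join, the bias is close to zero. The larger figures belong to the null PFS rates, where the primary test would most likely fail and, under Section 9.3, the approach would be reconsidered anyway. In germinoma, where most relapses are said to be salvaged, fewer deaths are at stake. The 45% is a ratio of two 2-year rates from a trial that also enrolled non-localized patients, not a measured mortality after relapse. The case report forms are posted elsewhere and might ask for survival status. All of this stands as a limit on size and priority. None of it removes the conflict between the follow-up rule and the OS objectives, or changes the direction of the bias.

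Two stronger readings are tempting and should not be made. A reader might infer that all deaths after relapse are lost. They are not: relapsed patients treated outside a COG therapeutic study stay in follow-up until death or the fifth anniversary of enrollment, barring loss to follow-up or withdrawal of consent. A reader might also infer that OS cannot be compared fairly with ACNS0122. That depends on the off-study and censoring rules of ACNS0122, which the documents do not give; if it used the same rule, both estimates would share the bias.

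**Conclusion.** The point holds in a limited form. Sections 8.1 and 8.2(c), followed as written, censor for OS the relapsed patients who join another COG treatment study, and Kaplan-Meier OS then reads too high whenever any of them would have died within the follow-up period. At the design PFS rates, with 45% mortality after relapse and up to half of relapsed patients joining, the 3-year bias is at most about 1.5 points and below one standard error. At 75% joining it is about one standard error. At the null PFS rates with half joining it is 2.8 to 3.8 points. Both driving inputs are assumptions, so these figures show a range and are not a forecast. Only descriptive, exploratory estimates are affected. The change is still worth making, because the error always favours the reduced treatment and comes from a rule that is easy to amend.

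**What to change.** Amend 8.2(c) so that joining another COG therapeutic study ends protocol evaluations but not collection of vital status and date of death. Continue that collection to the fifth anniversary of enrollment unless consent is withdrawn, by a query to the treating site or by linkage to the later study. Section 3.1.1 suggests that linkage is feasible: "The COG patient ID number is used to identify the patient in all future interactions with COG". Use these data in the OS analyses of 1.2.1 and 1.2.2, state the OS censoring rule in Section 9.1, and report how many patients leave under 8.2(c).

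The cost is one amended criterion and an annual status query for a few patients, with no added visit or procedure. At the design and null PFS rates, about 5 to 14 of 77 (77 × 0.07 to 77 × 0.18) and 4 to 10 of 79 (79 × 0.05 to 79 × 0.13) would relapse, and only those who join another COG study need the query. OS may read slightly less favourably.

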9.0 STATISTICAL CONSIDERATIONS

9.1 Study Design

The primary objective of the NGGCT stratum 1 is to test whether the subset of NGGCT patients who have a CR or PR in response to induction chemotherapy or who undergo second-look surgery after induction therapy and are found to have only mature teratoma, residual scar or fibrosis can be safely treated with 30.6 Gy WVI and IFR boost up to 54 Gy. The “intent-to-treat” principle will be followed and any eligible patient who receives dose and volume reduced radiation therapy and is evaluable based on response to induction therapy will be included in the primary analysis. The number of patients enrolled in stratum 1 who fail to receive this reduced radiation therapy will also be reported

The primary objective of stratum 2 is to test whether the PFS distribution of localized primary CNS germinoma patients who present with serum and or CSF hCG β \leq 50mIU/ml is sufficient to support continued investigation of the proposed treatment regimen. The “intent-to-treat” principle will be followed and any eligible patient who receives dose-reduced radiation therapy will be included in the primary analysis. The number of patients enrolled in stratum 2 who fail to receive this reduced radiation therapy will also be reported.

In addition, for each stratum descriptive statistics will be provided reporting the proportion of patients who are classified as local, ventricular, distant or a combination of local, ventricular, and/or and distant failures based primarily on imaging evaluation of the neuraxis. See [Section 15.12](#).

The first step in assessing primary objective 1.1.3, modeling neurocognitive function, as assessed on ALTE07C1, will be to monitor the rate of participation of eligible patients treated with dose and volume reduced radiation therapy in stratum 1 and dose-reduced radiation therapy in stratum 2. The same monitoring rule described below will be independently implemented for Stratum 1 and for Stratum 2.

Assessing neurocognitive function for patients treated on ACNS1123 will be considered feasible unless statistical evidence develops that fewer than 80% of patients who are eligible and evaluable for assessing primary objectives 1.1.1 or 1.1.2 and who are failure free at three years post initiation of therapy can be expected to have both 9-month and 30-month neurocognitive assessments on ALTE07C1. This rate of success will ensure that longitudinal modeling of neurocognitive function will provide viable historical controls for subsequent COG trials of these diseases. The rate of also achieving 60-month (5-year) neurocognitive assessments is not considered for monitoring feasibility, as the total study duration is only expected to be approximately seven years.

The statistical criteria for monitoring neurocognitive evaluations are based on a one-sided test ($\alpha = 0.025$) that the true, unknown, success rate is at least 80% ($\geq 80\%$) with 80% statistical power to detect that the success rate is 65%, which would be unacceptable. Assuming a binomial distribution, EAST5 was used to calculate the two stopping boundaries. If within a stratum, 9 (≤ 9) or fewer of the first 23 patients evaluable for feasibility (39.1%) have both 9 and 30 month evaluations (i.e. patients who are eligible and evaluable for assessing the primary objective and are more than 30 ± 4 months from

diagnosis), we will recommend to the COG DSMB that consideration be given to closing the stratum. The second boundary for recommending closing the stratum will be if 28 or fewer (≤ 28) of the initial 45 patients evaluable for feasibility (62.2%) enrolled in that stratum have both 9 and 30 month evaluations (i.e. patients who are eligible and evaluable for assessing the primary objective and are more than 30 ± 4 months from diagnosis). Otherwise accrual to the stratum will continue until the full cohort of patients required to address the primary objective assessing the 3-year progression-free survival rate has been achieved.

Our ability to address the secondary objectives depends upon whether the proposed treatment regimen is effective or not. Secondary objectives will be reported descriptively and as exploratory. Other than reports requested by the COG DSMB, secondary objectives will only be analyzed at the end of the trial.

1. The first secondary objective is to provide Kaplan-Meier estimates of distributions of PFS and overall survival for NGGCT patients.
2. The second secondary objective is to provide Kaplan-Meier estimates of the PFS and survival distributions of the cohorts of patients who present with a) non metastatic CNS Germinoma patients with $\text{hCG}\beta \leq 50$ mIU/ml and b) non metastatic CNS Germinoma patients with $\text{hCG}\beta > 50$ mIU/ml and ≤ 100 mIU/ml. These estimates will only be available to the COG DSMC until the trial is closed to accrual.

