9.2.2 Stratum 2 Germinoma

Based on the publication by Keene et al, the 95% confidence interval estimate of the incidence of CNS germinoma in children 4 to <18 years of age is (0.48, 0.91).⁶⁷ We assume that this estimate holds for 5 to 19 year olds. Canada and US population estimates for 5 to 19 year olds are 6.02 and 61.7 million, respectively. Thus, annually we estimate that there are 32.5 to 61.6 diagnoses of CNS germinomas in patients 5 to 19 years of age. Again based on Keene et al, approximately 77% of patients with CNS germinomas will be diagnosed with localized disease and approximately 75% will present with serum and CSF $\text{hCG}\beta \leq 50$ mIU/ml.⁶⁷ Assuming that 80% of eligible patients would consent to enrolling on this study, we estimate that the annual accrual for patients eligible for the primary study objective will be between 15 and 28 patients. Since 64.7% of eligible patients are expected to be evaluable for the primary objective, annual accrual of eligible, evaluable patients will be between 10 and 18 patients.

Due to the excellent accrual rate of germinoma patients within the initial 2.5 years of study opening (accrual of 80 patients within 27 months), we expect that approximately 5 years will be required as originally estimated to accrue the required 79 eligible patients evaluable for the primary objective. Note that assessing whether the accrual rate is adequate should not begin until one year after the protocol has been released to COG institutions for submission to their Institutional Review Boards (IRB). Receiving IRB approval takes significant time and thus accrual during the first year will no doubt be much less than projected; thus, assessment will begin with the completion of year two.

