9.3.3 Longitudinal Modeling of Neurocognitive Function (Cognitive, Social and Behavioral)

These analyses will be conducted independently for Stratum 1 (NGGCT) and Stratum 2 (Germinoma) patients. To be included in the analyses, patients must have the 9-month baseline assessment and at least one of either the 30-month or 60-month assessments.

The ALTE07C1 standard neuropsychological and behavioral battery focuses on three cognitive domains: intelligence, attention, and memory, as well as broad domains of social, emotional, and behavioral functioning. Data for all assessments will be available as standardized t-scores. The change over time for each component of the neuropsychological testing will be estimated using Generalized Estimating Equation (GEE);⁸² with the standardized t-scores as the dependent variable and the assessment times as a covariate. For neuropsychological components for which some patients are missing data at one of the three assessments, Weighted GEE⁸³⁻⁸⁴ will be used to address the missingness under the assumption that the data are missing at random (MAR).

GEE models will be used to explore associations of changes over time with factors such as gender, age at initiation of radiation therapy, tumor location, surgical intervention, etc.

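### The two printed neurocognitive-feasibility boundaries have one-sided alpha 0.0044 and 40% power at a 65% completion rate, not the stated 0.025 and 80%, and no further feasibility test is printed.

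*Combined protocol and SAP*

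**What the plan says.** Section 9.1 attaches one decision rule to primary objective 1.1.3, applied separately in each stratum. Neurocognitive assessment "will be considered feasible unless statistical evidence develops that fewer than 80% of patients" in the target group can be expected to have both the 9-month and the 30-month assessment. The criteria are based on a one-sided test at alpha 0.025 that the completion rate is at least 80%, "with 80% statistical power to detect that the success rate is 65%, which would be unacceptable".

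The section assumes a binomial distribution and says that "EAST5 was used to calculate the two stopping boundaries". The first is crossed if 9 "or fewer of the first 23 patients evaluable for feasibility (39.1%) have both 9 and 30 month evaluations". For the next, "The second boundary for recommending closing the stratum will be if 28 or fewer" of the initial 45 have both. Crossing either leads to a recommendation that the DSMB consider closing the stratum. If neither is crossed: "Otherwise accrual to the stratum will continue until the full cohort of patients required to address the primary objective" has been reached.

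No third boundary, final feasibility test or maximum sample size for feasibility appears in Sections 9.1, 9.3.3 or 16.0.

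**The concern.** Alpha and power belong to a complete decision rule, and the only rule in print is the pair of boundaries. Both cut-offs look too low for the stated figures: 28 of 45 is 62.2%, below the 65% rate that the rule is meant to detect, so at a true 65% a stratum would more often than not stay above it.

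Feasibility is presumed unless evidence against it appears, so low power works in favour of declaring success. Section 9.1 ties the 80% rate to producing usable historical controls for later trials. A DSMB that believes the rule has 80% power would take more reassurance from a pass than the rule can give.

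**Working it through.** **Inputs (all from Section 9.1).** Null completion rate 0.80; unacceptable rate 0.65; one-sided alpha 0.025; power 0.80; binomial distribution; look 1 flags if X₂₃ ≤ 9; look 2 flags if X₄₅ ≤ 28.

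**Check of the method on the plan's own PFS designs (Sections 9.3.1 and 9.3.2).** For Stratum 1, P(X ≥ 69 | n = 77) is 0.0492 at 0.82 and 0.911 at 0.93, exactly as printed. For Stratum 2, P(X ≥ 73 | n = 79) is 0.098 at 0.87 and 0.900 at 0.95, in line with the targets of 0.10 and 90%. Exact binomial calculation therefore reproduces the plan elsewhere.

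**The two feasibility looks.** With X₂₃ ~ Bin(23, p) and an independent increment Y ~ Bin(22, p) between the looks,

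P(flag) = P(X₂₃ ≤ 9) + Σ over x from 10 to 23 of P(X₂₃ = x) · P(Y ≤ 28 − x).

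| True rate | Flag at look 1 | Flag at look 2 | Total | Stated |
|---|---|---|---|---|
| 0.80 | 0.00002 | 0.00443 | 0.0044 | 0.025 |
| 0.70 | 0.0021 | 0.1621 | 0.164 | – |
| 0.65 | 0.0100 | 0.3917 | 0.402 | 0.80 |
| 0.60 | 0.0349 | 0.6379 | 0.673 | – |

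Neither stated figure is reproduced. At a true 65% the probability of passing both looks is 1 − 0.402 = 0.598.

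**Other cut-offs at 45, with the first look kept.**

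| Cut-off at 45 | Alpha at 0.80 | Power at 0.65 |
|---|---|---|
| ≤ 28 (printed) | 0.0044 | 0.402 |
| ≤ 29 | 0.011 | 0.525 |
| ≤ 30 | 0.0250 | 0.647 |
| ≤ 31 | 0.052 | 0.756 |
| ≤ 32 | 0.099 | 0.845 |

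No row meets both 0.025 and 0.80, so a misprinted second cut-off cannot be the explanation.

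**A possible third look.** I kept both printed looks, added one final look at every n from 46 to 79, and required alpha ≤ 0.025 and power ≥ 0.80. Seven designs qualify.

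| Final look | Alpha | Power |
|---|---|---|
| ≤ 47 of 68 | 0.0231 | 0.8006 |
| ≤ 49 of 71 | 0.0201 | 0.8001 |
| ≤ 50 of 72 | 0.0233 | 0.8218 |
| ≤ 52 of 75 | 0.0202 | 0.8209 |
| ≤ 53 of 76 | 0.0233 | 0.8405 |
| ≤ 54 of 78 | 0.0177 | 0.8203 |
| ≤ 55 of 79 | 0.0203 | 0.8395 |

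The stated figures can be reached with a third look, but the text does not identify which one.

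**What 65% completion would mean.** Expected failure-free patients are 77 × 0.93 ≈ 72 in Stratum 1 and 79 × 0.95 ≈ 75 in Stratum 2. At 65% completion about 47 and 49 would have both assessments; at 80%, about 57 and 60.

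**Timing of the 45-patient look (side point).** Time = 45/rate plus 26 to 34 months, assuming uniform accrual. The Stratum 1 rate is 49/53 × 12 = 11.09 per year. For Stratum 2, Section 9.2.2 says "annual accrual of eligible, evaluable patients will be between 10 and 18 patients", and its 79 patients in 5 years gives 15.8 per year.

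| Scenario | Look 2 (years) | Accrual ends (years) |
|---|---|---|
| Stratum 1, 11.09/yr | 6.2–6.9 | 77/11.09 = 6.9 |
| Stratum 2, 10/yr | 6.7–7.3 | 79/10 = 7.9 |
| Stratum 2, 15.8/yr | 5.0–5.7 | 79/15.8 = 5.0 |
| Stratum 2, 18/yr | 4.7–5.3 | 79/18 = 4.4 |

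In two scenarios the look comes before accrual ends, though in Stratum 1 by less than nine months. In the other two it comes at or after the end. Its value for closing accrual is limited, but not nil.

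**The case against.** The strongest reply is that the stated alpha and power belong to a whole design of which the printed boundaries are only the interim part. The numbers support this. 23 and 45 are about one third and two thirds of 68, and 47 or fewer of 68 gives 0.023 and 0.80. O'Brien-Fleming-type spending of a one-sided 0.025 allows about 0.0001 and 0.0060 cumulatively at those fractions. The printed looks spend 0.00002 and 0.0044, and 28 is the largest cut-off at 45 that stays within 0.0060. On this reading nothing was miscalculated; a final look was left out of the text. That is the likelier explanation, but it remains an inference. Section 9.1 speaks of two boundaries, names no final test, and goes straight from the second look to completing accrual. The part of the rule that would supply half of the claimed power is missing, and a cut-off chosen once completion data are known would not be prespecified.

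The second reply is that little depends on the rule, and much of that stands. A crossing prompts only a recommendation, and the PFS tests do not depend on it. The Section 9.3.3 models run in any case and are more lenient on entry: "patients must have the 9-month baseline assessment and at least one of either the 30-month or 60-month assessments". Weighted GEE is planned for missing assessments. The loss from 57 to 47 patients comes from poor completion itself; what the weak rule costs is the chance of detecting it.

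**Conclusion.** The concern holds. As printed, the rule has one-sided alpha 0.0044 and power 0.40, against the stated 0.025 and 0.80, and a stratum at 65% completion escapes notice about 60% of the time. Either a final look and its cut-off are missing from the text, or the stated alpha and power do not describe the rule; the documents do not show which. The calculation assumes independent patients with a common completion rate and looks at exactly 23 and 45 patients, as the plan itself does.

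It should be fixed, because this is the only decision rule for a primary objective. It does not threaten the PFS conclusions.

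**What to change.** Check the EAST output first, then do one of the following.

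- **(a) Print the final look** and its cut-off, and say that it governs whether objective 1.1.3 is declared feasible. For illustration, 47 or fewer of 68 gives overall alpha 0.023 and power 0.80. Add a fallback in case fewer patients qualify, such as 44 or fewer of 64 (0.023, 0.78) or 41 or fewer of 60 (0.023, 0.75).
- **(b) Keep two looks** and restate alpha as 0.004 and power as 40%, or move the second cut-off to 30 or fewer of 45 with alpha 0.025 and power 65%.

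Option (a) is preferable if the EAST output contains a final look, because it keeps the stated power. In either case, say whether the denominator is every evaluable patient past the 30-month window or only those failure-free at three years, since Section 9.1 uses both.

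The cost is text only, with no added enrolment. Under (a), a look after accrual can govern only the feasibility declaration, and 68 patients are not assured on the stricter, failure-free denominator. P(at least 68) in Stratum 1 (n = 77) is 0.96 if 3-year PFS is 93% and 0.09 if it is 82%. In Stratum 2 (n = 79) it is 0.999 at 95% and 0.67 at 87%. Under (b), the sponsor accepts 40% or 65% power, and the 30-of-45 cut-off raises the false-flag rate from 0.004 to the planned 0.025.

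A separate minor point: Section 9.1 expects the whole study to last about seven years, while Section 9.2.1 needs about 7 years for Stratum 1 accrual alone, before three years of follow-up. The two should be reconciled.
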